14.2.5 Subgroup Analyses

Subgroup analyses for secondary endpoints of DoR, PFS and OS will be performed by cohort and assigned dose level of tepotinib for all the baseline subgroup levels identified in Section [8.2](#).

The Kaplan-Meier based analysis described in Section [14.2.2](#) will be repeated for all the baseline subgroups. The same rules described in the first paragraph of Section [14.2.2](#) will apply.

CCI

15

Safety Analyses

The analysis of the primary safety endpoint will be performed on the DLT analysis set whereas the analyses of the secondary safety endpoints will be performed on the SAF analysis set.

In case the RP2D for tepotinib is 250 mg and there are participants who started on the 500 mg dose, a selection of the safety tables may be repeated on these participants, otherwise their data will only be listed.

The safety analyses will be done purely descriptively.

15.1

Primary Endpoint (Safety Run-in): Occurrence of DLTs

The number and percentage of participants in the DLT analysis set with no DLT, 1 DLT or 2 or more DLTs observed during the DLT observation period will be tabulated together with the respective SOCs and PTs as well as the number of participants with any TEAE during cycle 1.

All DLT relevant data will also be listed.

DLT evaluation by the Investigator as well as by the SMC will be available for the analyses. In the "Adverse Event Details" eCRF page, the question "Is this adverse event a dose limiting toxicity" will

be used to identify the DLTs within 21 days after start of study treatment (DLT observation period) by Investigator assessment. SMC decisions will be implemented programmatically into SDTM dataset based on SMC feedback received.

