#### 9.4.2 Safety Analyses

All safety analyses will be performed on the Safety Analysis population unless otherwise specified. All analyses will be presented by cohort and dose level, if applicable. The safety analyses will also be done purely descriptively. Further details will be provided in the IAP.

Endpoint	Statistical Analysis Methods
Primary	
Occurrence of DLTs	The number and percentage of participants in the DLT analysis set during the DLT observation period will be tabulated.
Secondary	
Occurrence of Adverse Events (AEs) and treatment-related AEs	
Adverse events will be coded according to the latest available version of the Medical Dictionary for Regulatory Activities version 21.0 or higher. Severity of AEs will be graded using the NCI-CTCAE (v5.0) toxicity grades. Adverse events related to study intervention will be defined as any AE considered as related to tepotinib and/or cetuximab. Missing classifications concerning study intervention relationships will be considered related to the study intervention.
 
Any TEAEs will be summarized, i.e., those events that are emergent during treatment having been absent prior to treatment or worsened relative to the pretreatment state and with onset dates occurring within the first dosing day of study intervention until 30 days after the last dose of study intervention.
 
Following subtypes of TEAEs will be presented in summaries and tables according to System Organ Classes and Preferred Terms:
 
 
• TEAEs
 
• SAEs
 

Endpoint	Statistical Analysis Methods

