8.1 Definition of Analysis Populations

The analysis populations are specified below. The final decision to exclude participants from any analysis population will be made during a data review meeting prior to database lock.

Screening Analysis Set (SCR)

The Screening analysis set includes all participants, who provided informed consent, regardless of the participant's study intervention status in the study.

Full Analysis Set (FAS)/ Safety Analysis Set (SAF)

These analysis sets will include all participants, who were administered at least one dose of any study intervention.

Dose Limiting Toxicity Analysis Set (DLT)

The Dose Limiting Toxicity analysis set (DLT) will include all participants who received at least one dose of study treatment in the safety run-in period and meet at least one of the following criteria:

- Received at least 75% of the tepotinib and cetuximab planned dose and complete the DLT period (3 weeks after start of treatment with study intervention).
- Experienced a DLT during the DLT period, regardless of the received amount of each study intervention.

Pharmacokinetics Analysis Set (PKAS)

The pharmacokinetics analysis set will include all participants, who received at least one dose of study intervention, have no relevant protocol deviations or important events affecting PK, and provide at least one measurable post-dose concentration. Participants will be analyzed per the actual study intervention they received.

Immunogenicity Analysis Set (IMAS)

All participants who receive at least one dose of study intervention and have at least one valid ADA result. Participants will be analyzed per the actual study intervention they received.

Analyses per Analysis Set

The following table summarizes the use of the analysis sets in the different analyses.

	Analysis Set				
Analyses	DLT	FAS	SAF	PK	IMAS
DLT	✓				
Baseline Characteristics		✓			
Previous and Concomitant Therapies		✓			
Compliance and Exposure			✓		
Efficacy: Primary		✓			
Efficacy: Secondary		✓			
Safety and Tolerability			✓		
PK				✓	
Immunogenicity					✓

DLT = Dose Limiting Toxicity; FAS = Full Analysis Set; SAF = Safety Analysis Set; PK = Pharmacokinetics; IMAS = Immunogenicity Analysis Set.

All safety analyses will be presented by cohort and dose level, if applicable. Efficacy analyses will be done by cohort and assigned dose level of tepotinib.

For more details see Section 0 General Specifications for Data Analyses.

8.2

Subgroup Definition and Parameterization

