This section describes any general specifications not included in subsequent sections.

Study treatment and study treatment component:

Participants will receive tepotinib (RP2D mg daily) in combination with cetuximab (loading dose (where required) 400 mg/m², followed by or starting with weekly infusions at a dose of 250 mg/m²).

In this IAP, “study treatment” will be used to indicate the combination of tepotinib and cetuximab; “study treatment component” will be used to refer to tepotinib or cetuximab.

Study treatment start date:

For each participant, the “start date” of this study is the date of first administration of the study treatment. If, for any reason, the first administration of tepotinib and cetuximab does not happen on the same day, the date of administration of the first study treatment component taken should be considered as the “start date”.

Study treatment end date:

The last tepotinib and cetuximab administration dates are collected on the “Tepotinib Termination” and “Cetuximab Termination” eCRF pages. These should be considered the dates of permanent discontinuation of tepotinib and cetuximab respectively.

The end of study treatment will be the last study tepotinib administration date or the last study cetuximab administration date, whichever comes later.

Dose Level:

As stated in Section 6.1, the SMC will decide whether the tepotinib 500 mg dose level is considered safe or if the 250 mg dose level should be used instead. Cetuximab will be administered as intravenous infusion as detailed in protocol Section 6.1.

Cohort:

Cohort A – includes participants outside of US for 2L treatment.

Cohort B – includes US participants for 3L+ treatment.

Presentation of analysis results:

Unless stated otherwise, for disposition, baseline characteristics (e.g. demographics, medical history, disease history, etc.), previous and concomitant medications and procedures, results will be presented by cohort, by assigned dose level of tepotinib and overall.

For efficacy analyses, results will be presented by cohort and assigned dose level of tepotinib.

Exposure and safety will be presented by cohort and dose level, if applicable, and overall.

Presentation of continuous and qualitative variables:

Continuous variables other than PK will be summarized using descriptive statistics, i.e.

- number of participants with non-missing values (n)
- mean, standard deviation (StDev)
- median, 25th percentile - 75th percentile (Q1-Q3)
- minimum, maximum

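### If 250 mg becomes the recommended dose, SAP Section 15 makes the general safety tables for participants who started on 500 mg optional, against the plan's own safety set and presentation rules

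*SAP*

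**What the plan says.** The rule is in the opening paragraphs of SAP Section 15 (Safety Analyses). Its trigger is "In case the RP2D for tepotinib is 250 mg and there are participants who started on the 500 mg dose". Its consequence is that "a selection of the safety tables may be repeated on these participants, otherwise their data will only be listed".

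Four other places bear on it:

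- The paragraph just before it in SAP Section 15 says that "the analyses of the secondary safety endpoints will be performed on the SAF analysis set".
- SAP Section 8.1 defines the full and safety sets together: "These analysis sets will include all participants, who were administered at least one dose of any study intervention". Nothing restricts them to the RP2D.
- SAP Section 9, on presentation of results: "Exposure and safety will be presented by cohort and dose level, if applicable, and overall".
- Protocol Section 9.4.2 places the safety analyses on the safety population and adds: "All analyses will be presented by cohort and dose level, if applicable".

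SAP Section 15.1 handles DLTs separately. It tabulates "The number and percentage of participants in the DLT analysis set with no DLT, 1 DLT or 2 or more DLTs observed", with system organ classes and preferred terms, and adds the number of participants with any treatment-emergent event in Cycle 1.

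**The concern.** A table can be repeated on a group only if that group is not already shown in it, and listing is what happens unless someone decides otherwise. On its plain reading, the rule leaves the 500 mg starters out of the general safety tables unless the sponsor chooses to add some. The trial is open-label, so that choice could be made with the events known.

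The trigger is not neutral. Participants will have started on 500 mg and the RP2D will be 250 mg only if the DLT boundary was crossed at 500 mg or the Safety Monitoring Committee reduced the dose on run-in data. Any omission would therefore be linked to toxicity. Safety and tolerability of the combination is a stated secondary objective, and the summary tables are what most readers will use to judge it.

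Efficacy has no matching exception. SAP Section 14 reports response by cohort and assigned dose level. The same participants would thus be tabulated for response, while tables of their adverse events are optional. SAP Section 7, on changes from the protocol analyses, contains only COVID-19 text and does not declare this one.

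**Working it through.** **1. The passages side by side, when the RP2D is 250 mg**

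| Source | Where 500 mg starters appear |
|---|---|
| SAP 8.1 | In the safety set, like anyone dosed |
| SAP 9 | In a dose-level column and in the overall column |
| Protocol 9.4.2 | In the safety population, shown by dose level |
| SAP 15, first paragraph | In the secondary safety analyses, as members of the safety set |
| SAP 15, conditional rule | In listings; tables at discretion |
| SAP 15.1 | In the DLT table, which also gives any Cycle 1 event |
| SAP 15.4, 15.5, 15.6.2 | Run-in laboratory, vital-sign and ECG data taken in |
| SAP 15.2, 15.3 (adverse events, deaths) | No corresponding run-in statement |

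The first four rows and the fifth cannot all be followed. The tables left open are chiefly the adverse event tables.

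**2. Size of the group**

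Inputs: run-in cohorts of 3 (Protocol 9.4.2.1); at most 6 participants per dose level in the run-in (Protocol Appendix 8); 42 participants at the RP2D and at most 48 treated (Protocol 9.2).

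- De-escalation after the first cohort: 3/(3 + 42) = 3/45 = 6.7%.
- De-escalation after the second cohort: 6/(6 + 42) = 6/48 = 12.5%.

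If the boundary caused the change, at least 2 of 3 (67%) or 3 of 6 (50%) had a DLT.

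As an illustration, suppose 3 of 6 participants at 500 mg had some event and the 42 others had it at rate r. The overall rate is then (42r + 3)/48. For r = 10%, 20% and 30% this gives 15.0%, 23.75% and 32.5%. Leaving the group out would understate the overall rate by 5.0, 3.75 and 2.5 percentage points.

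**3. The plan's de-escalation boundary**

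Protocol 9.4.2.1 gives de-escalation at 1, 1, 2, 2, 2 and 3 or more DLTs for 1 to 6 participants, with a target rate of 30%. The interval limits are not printed in the text available. I assume the usual defaults, 0.6 and 1.4 times the target (0.18 and 0.42). The de-escalation limit is

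ln(0.70/0.58) / ln[(0.42 × 0.70)/(0.30 × 0.58)] = 0.3585.

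Rounding 0.3585n up gives 1, 1, 2, 2, 2, 3, which matches the table.

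**4. Chance of crossing the boundary at 500 mg**

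With looks at 3 and 6 participants, X DLTs in the first three and Y in the next three:

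P(cross) = P(X ≥ 2) + P(X = 0)·P(Y = 3) + P(X = 1)·P(Y ≥ 2)

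- True rate 20%: 0.104 + 0.512 × 0.008 + 0.384 × 0.104 = 0.148
- True rate 30%: 0.216 + 0.343 × 0.027 + 0.441 × 0.216 = 0.321
- True rate 40%: 0.352 + 0.216 × 0.064 + 0.432 × 0.352 = 0.518

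**5. From crossing to an RP2D of 250 mg**

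The 9.4.2.1 footnote applies the same scheme at 250 mg as a stopping rule, so 250 mg must also stay below it. Multiply by 1 − P(cross) at the 250 mg rate:

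| 500 mg DLT rate | Crossing at 500 mg | 250 mg rate half | 250 mg rate equal |
|---|---|---|---|
| 20% | 14.8% | 14.3% | 12.6% |
| 30% | 32.1% | 29.4% | 21.8% |
| 40% | 51.8% | 44.1% | 25.0% |

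The table also allows escalation back to 500 mg, which would lower the last two columns further.

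**The case against.** A reader might infer that SAP Section 15 simply removes the 500 mg starters, so that the toxicity that forced the de-escalation would be seen only in listings. The documents do not support that. SAP 15.1 tabulates DLTs on the DLT set, and SAP 8.1 admits to that set any run-in participant who "Experienced a DLT during the DLT period, regardless of the received amount of each study intervention". The triggering events are therefore planned to be in a table, and the run-in laboratory, vital-sign and ECG data are brought in as well.

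Nor does any text redefine the safety set or take anyone out of the overall column. The repeated tables could be read as optional stand-alone outputs, added to main tables that already contain everyone. On that reading the plan is inconsistent, and no biased analysis has been chosen. Safety is descriptive throughout, the group is at most 6 people, and individual listings would show their events. SAP Section 6.4 refers to a table of contents for the outputs, which is not in the documents and might name the selection.

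Much of this stands, and it limits the point to an unresolved contradiction. It does not remove it. The stand-alone reading fits poorly with the statement that the data would otherwise only be listed. The DLT table covers 21 days, states no split by dose, and gives no rates for Grade 3 or higher, serious or discontinuation events or for later cycles. Listings do not supply rates.

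**Conclusion.** The concern holds as a conflict within the plan with a practical consequence. If the RP2D is 250 mg, SAP Section 15 makes the general safety tables for 500 mg starters optional and gives no criterion. That contradicts SAP 8.1, SAP 9 and Protocol 9.4.2. If the rule is followed as written, adverse event summaries beyond the DLT table could omit 3 to 6 participants, for a reason tied to toxicity. It would be too strong to say that these participants are definitely dropped or that the safety objective is necessarily biased, because the SAP does not settle which instruction prevails.

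The group size assumes full enrolment of 42 at the RP2D, run-in cohorts of 3, and no extra participants dosed as replacements. The crossing probabilities of 14.8%, 32.1% and 51.8% assume true DLT rates of 20%, 30% and 40%. They should not be read as the probability that 250 mg becomes the RP2D. For de-escalation driven by the boundary they are an upper guide, and they do not cover a reduction that the committee makes on other grounds. The situation is plausible enough to settle in advance.

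**What to change.** Replace the conditional rule in SAP Section 15 with: *All safety tables on the SAF are produced by cohort, by starting tepotinib dose level (500 mg and 250 mg) and overall, with every dosed participant in the overall column.*

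Add to SAP Section 15.1 that the DLT table is split by dose level.

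This restores what SAP 8.1, SAP 9 and Protocol 9.4.2 already state. The cost is one replaced SAP sentence, a short addition to 15.1 and, only if 250 mg is chosen, one more column in the tables. It changes reporting only and affects no dose decision.

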15.2 Secondary Endpoints

15.2.1 Adverse Events

Adverse events will be coded according to the Medical Dictionary for Regulatory Activities (MedDRA; latest version at the time of database lock for each analysis will be used and be specified in outputs). Severity of AEs will be graded using the NCI-CTCAE (Version 5.0) toxicity grades.

Relationship with the study treatment components are collected in the “Adverse Events Details” eCRF page. Adverse Events can be related to tepotinib, cetuximab or both. In case the relationship information is missing for a study treatment component, the AE will be considered as related to that component.

Incomplete AE-related dates will be handled as specified in Section [9.8](#).

Treatment emergent adverse events (TEAE) are those events that occurred during on-treatment period, having been absent prior to treatment or worsened relative to the pre-treatment state and with onset dates occurring within the first dosing day of study intervention until 30 days after the last dose of study intervention.

For the Adverse Event that started before the first administration of study treatment, the latest toxicity grade before first dose will be considered as the baseline grade and used to assess whether the AE worsens during the on-treatment period.

Pre-existing conditions continuing on-treatment with grade equal or lower than the baseline grade will not be considered as TEAEs.

All analyses described in Section [15.2.2](#) and [15.2.3](#) will be based on TEAEs if not otherwise specified. The AE listings will include all AEs (whether treatment emergent or not). A flag will be added to indicate if the AE is treatment emergent (i.e. started or worsened between the date of first dose of the study treatment and the date of last dose + 30 days).

Unless otherwise specified, TEAEs will be summarized by number and percentage of participants with the TEAE in the category of interest and sorted by primary System Organ Class (SOC) and Preferred Term (PT) in alphabetic order.

Each participant will be counted only once within each SOC or PT. If a participant experiences more than one AE within a SOC or PT for the same summary period, only the AE with the strongest relationship or the worst severity, as appropriate, will be included in the summaries of relationship and severity.

15.2.2 All Adverse Events

Adverse Event information is collected on the “Adverse Events Details” eCRF page.

Adverse events will be summarized by worst severity (according to NCI-CTCAE version 5.0) per participant, using the latest version of MedDRA preferred term (PT) as event category and MedDRA primary system organ class (SOC).

In case a participant has events with missing and non-missing grades, the maximum of the non-missing grades will be displayed. No imputation of missing grades will be performed.

Incomplete AE-related dates will be handled as specified in Section 9.8.

The overall summary of AEs table will include the frequency (number and percentage) of participants within the following categories:

- TEAEs
- Study treatment related TEAEs (any study treatment and by study treatment components)
- Serious TEAEs
- Study treatment related serious TEAEs (any study treatment and by study treatment components)
- TEAEs with NCI-CTCAE Grade ≥ 3 and ≥ 4
- Study treatment related TEAEs with NCI-CTCAE Grade ≥ 3 and ≥ 4 (any study treatment and by study treatment components)
- TEAEs leading to death
- Study treatment related TEAEs leading to death (any study treatment and by study treatment components)
- Adverse Events of Special Interest (AESIs)

Adverse events of special interest are defined as events suggestive of drug-induced liver injury including hepatic / liver failure and hepatitis (non-infectious). The question “Is this an adverse event of special interest” present on the “Adverse Event Details” eCRF page will be used to identify these AEs.

In addition, the following tables summarizing the frequency of participants with TEAEs by SOC and PT will be produced:

- TEAEs
- Study treatment related TEAEs (any study treatment and by study treatment components)
- Serious TEAEs
- Non-serious TEAEs applying a frequency threshold of 5%

- Study treatment related serious TEAEs (any study treatment and by study treatment components)
- TEAEs by worst NCI-CTCAE Grade (Any, ≥ 3 , ≥ 4 and 5)
- Study treatment related TEAEs by worst NCI-CTCAE Grade (Any, ≥ 3 , ≥ 4) (any study treatment and by study treatment components)
- TEAEs leading to death
- Study treatment related TEAEs leading to death (any study treatment and by study treatment components)
- Adverse Events of Special Interest (AESIs)

Participant listings of AEs details collected on the “Adverse Events Details” eCRF page will also be provided for each of the following:

- AEs
- AESIs
- Serious TEAEs

TEAEs frequency and worst grade for TEAEs occurring in $\geq 10\%$ participants will be plotted by cohort.

15.2.3 Adverse Events Leading to Discontinuation / Dose Reduction of Study Treatment

The frequency (number and percentage) of participants with each of the following will be presented in a summary table:

- TEAEs leading to temporary discontinuation of study treatment (any study treatment and by study treatment components)
- Study treatment related TEAEs leading to temporary discontinuation of study treatment (any study treatment and by study treatment components)
- TEAEs leading to permanent discontinuation of study treatment (any study treatment and by study treatment components)
- Study treatment related TEAEs leading to permanent discontinuation of study treatment (any study treatment and by study treatment components)
- TEAEs leading to dose reduction of study treatment (any study treatment and by study treatment components)
- Study treatment related TEAEs leading to dose reduction of study treatment, (any study treatment and by study treatment components)

In addition, tables summarizing the frequency of participants with AEs, presented by SOC and PT, in the above categories will be prepared. Tables summarizing TEAEs related to study treatment will be created to summarize TEAEs related to any study treatment and will be repeated to summarize TEAEs related to specific study treatment components (i.e. tepotinib and cetuximab).

Actions that can be taken by the Investigator to address an Adverse Event are collected by sections “Action(s) taken with Tepotinib” and “Action(s) taken with cetuximab” on the “Adverse Events Details” eCRF page. It is possible that a TEAE leads to more than one action: for example, a drug interruption followed by drug withdrawn. In this case the TEAE will be counted among the TEAEs leading to temporary discontinuation as well as among the TEAEs leading to permanent discontinuation.

Participant listings showing the relevant information will also be provided:

- AEs leading to permanent discontinuation of study treatment
- AEs leading to temporary discontinuation of study treatment

